## **4.2 Selection of Subjects**

Subjects will be recruited at MCW and OSU through referral from their treating Hematologist or Oncologist. The patient's treating physician will give potential participants the informational flyer (Appendix A) or use the flyer to verbally describe the study and receive permission for the patient to be screened for eligibility and contacted by the research coordinator. Additionally at Milwaukee and Columbus, an electronic alert will be created that identifies a person with catheter-related thrombosis through the results of their radiology report. The research coordinator will review the report and then contact the treating physician to inform them of the study and receive permission to contact the subject. In 2012, 2350 new patients were seen in the Heme/Onc and BMT clinics at Froedtert Hospital and 1003 had a Port-A-Cath placed. Estimating a catheter-associated thrombotic rate of 15%, this predicts approximately 150 patients annually with CRT due to a Port-A-Cath. Additional patients are anticipated due to CRT from peripherally inserted central catheters (PICC). A survey was conducted among the Heme/Onc and BMT physicians at MCW with a 60% response rate (21/35). The physicians estimated that 63 patients had been seen with CRT in the last 3 months (252 annual). 86% of physicians reported that they would refer patients to a study of CRT treated with 4 weeks of anticoagulation; 14% were uncertain. MCW physicians also noted a variety of treatment practice from 4 weeks to 3 months of anticoagulation after catheter removal. We estimate a 10% drop out rate due to reinsertion of a catheter or inability to remove a catheter. We also estimate that we will need to screen and approach 3 patients for every participant. Therefore, we will plan to screen and approach 250 patients to enroll 56 patients (36 BCW and, OSU 20,) and have 50 complete the study as the overall target.

## **4.3 Sample Size Estimates**

Sample size estimates were based on the confidence interval method and were based upon the feasibility endpoints. With 50 patients completing the study, we would have 95% confidence that completion of 80% of PTS assessments in the pilot study would correspond to 66-90% completion in another study. Completion of 90% of assessments

would correspond to between 78-96% of assessments. We estimate a 10% drop-out rate so will plan to enroll 56 patients over 1 year.

Evaluation of 50 patients would provide 95% confidence that if the feasibility study found a PTS incidence of 10% that the true proportion in a larger study would not be greater than 20%.

## **5. Clinical Procedures**

### **5.1 Enrollment and Consent**

We aim to consent and enroll participants after diagnosis of catheter-related thrombosis and prior to catheter removal. Participants must be consented and enrolled prior to anticoagulation discontinuation. Screening will be completed using Appendix B (Script Appendix B; Screening form Appendix C). Medical history, family history, and medications will be reviewed after consent is obtained (Appendices D-H). Consent for medical record release will be obtained to determine cancer staging and laboratory information from the time of CRT diagnosis.

### **5.2 Anticoagulation**

Participants will be treated with either enoxaparin for one month following catheter removal, or direct oral anticoagulant treatment (apixaban, rivaroxaban, dabigatran, or edoxaban). Dosing an alternate enoxaparin dose or interval based on anti-factor Xa testing that was obtained by clinical team, at standard dosing per FDA package insert. Anticoagulation will be continued for 1 month after catheter removal. The minimum duration of anticoagulation will be one month and maximum duration is 7 months. The cost of enoxaparin or direct oral anticoagulant treatment will be the responsibility of the participant as use of the medication is part of routine care. Subjects will be contacted by telephone prior to discontinuation of anticoagulation to review if any continuation rules apply and arrange for research visit 2.

### **5.3 Concomitant medications**

The decision of which anticoagulant to prescribe for the thrombotic event will be made by the patient's physician per standard of care. The patient's prescribing physician will be responsible for assessing the potential drug interactions between anticoagulant therapy and other medications as he or she would in their normal medical practice. For example, direct oral anticoagulant therapy medications have drug interactions with CYP3A4 inhibitors and inducers. Use of anti-platelet agents will be allowed and recorded. We anticipate the use of antiplatelet agents to be low because of the risk of thrombocytopenia associated with many chemotherapeutic agents.

### **5.4 Catheter removal**

The timing and mechanism of catheter or port removal will be directed by the subjects' treating physician. The practitioner type (ex. MD Interventional Radiologist vs RN PICC

Team) will be recorded. Additionally, the reason for catheter removal will be recorded. In a patient that requires catheter or port re-insertion while on enoxaparin or direct oral coagulant therapy, the enoxaparin or direct oral coagulant therapy will be continued for 30 days following removal of all catheters or ports provided the time of anticoagulation does not exceed 6 months duration. If a patient requires re-insertion of a catheter or port after discontinuation of enoxaparin or direct oral anticoagulant therapy, they will be removed from the study at that time because a new catheter would be an additional thrombotic inciting factor.

### 5.5 Post-thrombotic syndrome assessments

Visit 2 will occur within 2 weeks of discontinuation of anticoagulation. Visit 3 will be at 3 months after catheter removal plus or minus 2 weeks and Visit 4 within 6 months plus or minus 2 weeks after catheter removal. At each visit, medical history and medication will be reviewed (Appendices E-G). The subjective assessment of the modified Villalta (page 1 and 2 of Appendix I) and the DASH questionnaire (Appendix J) will be administered by the Translational Research Unit (TRU) staff or the clinical nurse coordinator after completing the objective assessment. The objective assessment of the modified Villalta score will be completed by trained clinical nurse coordinators blinded to the subjective assessment (page 3 and 4 of Appendix I). The subjective assessment of the modified Villalta (page 1 and 2 of Appendix I) and the DASH questionnaire (Appendix J), will be administered by the research coordinator at OSU.

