The catheter is removed if it is non-functioning or is no longer needed. The duration of anticoagulation in patients with catheter-related thrombosis has not been studied in a systematic fashion and is not standardized in clinical practice. A delicate balance exists between thrombosis and bleeding in cancer patients because cancer patients have 3 times higher risk of recurrent thrombosis and 2.5 times higher risk of major hemorrhage compared to non-cancer patients. Consensus guidelines have a weak recommendation for anticoagulation for 3 months after catheter removal in patients with upper extremity CRT (ACCP and ISTH guidelines attached). These recommendations are extrapolated from data on provoked lower extremity thrombosis, retrospective case series and two prospective cohort studies. Review of the literature reports treatment of catheter-related thrombosis ranging from catheter removal without anticoagulation to treatment with anticoagulation up to 6 months. In cancer patients, upper extremity CRT are often treated with anticoagulation for 4-6 weeks to balance the risks of thrombotic recurrence with bleeding. Additionally, extraction of the catheter removes an inciting factor for thrombosis which may allow for shorter duration of therapy. In a survey of MCW Heme/Onc physicians, treatment of patients with CRT ranged from 4 weeks to 3 months. A retrospective review of patients with hematologic malignancies from 2009-2011 found 85 patients with catheter-related thrombosis treated at MCW. Three patients (4%) were not treated for their CRT and 20 patients (24%) had the catheter removed only. Of the patients that underwent anticoagulation, the median total treatment duration was 42 days (range 3-1485 days). Of patients who had their catheter removed, the median treatment duration after catheter removal was 44 days (range 4-453 days). The retrospective study was not able to assess development of PTS due to lack of assessment as a part of routine practice. Overall, there is no standard treatment duration for patients with catheter-related thrombosis and 1 month of anticoagulation after catheter removal is within clinical practice at both locations. This multicenter prospective cohort pilot study project defines the duration of anticoagulation after catheter removal at one month to balance the risk of thrombosis with the risk of bleeding, patient cost and discomfort of injecting enoxaparin twice a day. The project will assess feasibility and obtain estimates of clinical outcomes including PTS, thrombosis recurrence, and bleeding. The feasibility outcomes will assess accrual, enrollment, and retention procedures. The data obtained from the pilot study will be used to provide sample size estimates for a larger definitive study. Additionally the

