### 3.5 Continuation of anticoagulation criteria

Participants will be continued on anticoagulation longer than one month after catheter removal if any of the following criteria exist:

1. Development of thrombosis other than the CRT
2. Extension of the catheter-related thrombosis (i.e. additional vein occlusion on imaging obtained for clinical reasons)

If an enrolled subject at MCW requires anticoagulation longer than 1 month after catheter removal, laboratory assessments will not be completed as the testing can be affected by the presence of an anticoagulant. The participant will not be removed from the study and will be followed for PTS outcomes.

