## 4. Study Design

### 4.1 Study Overview

[figure not shown]

Figure 1 shows the overall study design of the multicenter prospective cohort of cancer patients with catheter-related thrombosis. Participants may be referred for screening at MCW in two possible mechanisms: participant contact study staff from information on CTSI FACT website or referral from treating Hematologist or Oncologist. At MCW, an EPIC report will be generated to identify people with CRT. The treating provider would then be contacted to determine if referral to the study was appropriate. Subjects at OSU will be referred from the treating Hematologist or Oncologist. A report generated in Epic will be used to identify people with CRT. The treating provider would then be contacted to determine if referral to the study was appropriate. Participants will be given printed information about the study (Appendix A) or verbal explanation using the informational flyer. Verbal consent will be obtained to be screened for participation and contacted by study personnel. Screening will be completed by BCW nurse coordinator (Script Appendix B; Screening form Appendix C). We aim to consent and enroll patients after diagnosis of catheter-related thrombosis and prior to catheter removal. Consent and enrollment (Visit 1) must occur prior to discontinuation of anticoagulation. Enrollment will be limited to patients undergoing anticoagulation with either enoxaparin or a direct oral anticoagulant at the discretion of the treating provider. The study will follow patients treated with anticoagulation for one month after catheter removal. Prior to discontinuation of anticoagulation, patients will be contacted via telephone to review study protocol, assess for bleeding, and arrange for Visit 2 in the following 1-2 weeks. Appendices D-H include the background information that will be collected. Visits 3 and 4 will occur 3 and 6 months after catheter removal, respectively. At visits 3 & 4, Medical history, cancer history, and medications will be updated (Appendices E-G). At each visit, participants will be assessed for post-thrombotic

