### 5.6 Blood measurements

Blood will be collected by venipuncture using a 20G needle or larger from patients at the BCW site at Visit 2, 3 and 4. A 21G needle may be used for collection of blood via venipuncture if blood cannot be obtained with a 20G needle or larger. The first 2 ml of blood will be discarded due to tissue factor activation with the venipuncture. Three BD Vacutainer citrated tubes (0.105M sodium citrate) with 4.5 ml blood will be collected. Thrombin generation, D-dimer, plasma total TFPI and TFPI $\alpha$ , and platelet TFPI $\alpha$ , will be assayed using platelet-poor plasma (PPP). Thrombin generation will also be assayed using platelet rich plasma (PRP). Laboratory procedures as noted in section 6.

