## 7. Subject Remuneration

For their time and efforts in study activities, research subjects will receive \$25 for each of the following patient visits:

- Study visit 2, 1 month after catheter removal
- Study visit 3, 3 months after catheter removal
- Study visit 4, 6 month after catheter removal

A total of \$75 will be paid to subjects completing all study visits to cover travel to the research site, parking, and time of the visits. The subject will be paid \$25 for each completed study visit whether they withdraw, the investigator withdraws them or they complete all study activities. Payment will occur when they are no longer an active participant in the study. Remuneration for study visits will only take place at the BCW site.

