### **11.2 Statistical Analysis**

The incidence of PTS, thrombotic recurrence, major bleeding and clinically relevant non-major bleeding will be reported as proportions. These outcomes will be compared at 3 and 6 months using Chi-square or Fisher's exact tests. A Cox-proportional hazards model will be utilized to calculate the risk of PTS and thrombosis recurrence. Chi-square or Fisher's exact tests will be used to determine if clot presentation or location predicts PTS or thrombotic recurrence. Agreement between the DASH and QuickDASH scales will be assessed using the intraclass correlation coefficient. To compare the discriminating ability of the DASH and QuickDASH on the level of PTS, receiver operating curves will be developed using the scale scores at 6 months as the test variable and dichotomized PTS assessment as the classifying variable. Levels of D-dimer, thrombin generation, and TFPI will be reported as means. Logistic regression will evaluate if D-dimer, thrombin generation or TFPI levels at 1 month or % change from baseline predict thrombotic recurrence. Where necessary, for parametric assumption, we will employ appropriate transformations with justifications. For example, the log of some of the biomarkers data may be used if the data range is >1000. Statistical

significance will be determined with  $p < 0.05$ . SAS version 9.13 and JMP 10 Statistical software will be employed for data analysis.

An interim analysis will be completed after 20 patients complete 6 months of follow-up. The interim analysis will allow assessment of thrombotic recurrence by the DSMC.

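### The Visit 2 research blood draw has no minimum gap after the last anticoagulant dose, so early draws could distort the exploratory one-month biomarker level

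*Combined protocol and SAP*

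**What the plan says.** The timing of Visit 2 appears in three places in the combined protocol and SAP.

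- Section 5.5, which sets the visit windows: "Visit 2 will occur within 2 weeks of discontinuation of anticoagulation".
- Section 4.1, on a telephone call made before anticoagulation stops: staff will "arrange for Visit 2 in the following 1-2 weeks".
- Section 7, in the list of paid visits: "Study visit 2, 1 month after catheter removal". Section 5.2 puts the end of treatment at the same point: "Anticoagulation will be continued for 1 month after catheter removal".

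Section 5.6 has blood taken "from patients at the BCW site at Visit 2, 3 and 4", and Table 2 shows no draw at Visit 1, so Visit 2 is the first sample. Section 11.2 uses it as follows: "Logistic regression will evaluate if D-dimer, thrombin generation or TFPI levels at 1 month or % change from baseline predict thrombotic recurrence".

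For Milwaukee patients who stay on treatment beyond one month after removal, section 3.5 says that "laboratory assessments will not be completed as the testing can be affected by the presence of an anticoagulant".

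**The concern.** Section 3.5 gives the reason for wanting samples free of drug, but its rule covers only patients whose treatment is extended. For everyone else, section 5.5 permits a draw on the day treatment stops. Section 1 refers to the "discomfort of injecting enoxaparin twice a day", so a same-day draw can fall within one dosing interval.

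Sections 5.6 and 6 specify needle gauge, discard volume and centrifugation. They do not specify an interval from the last dose, a drug-level check or a neutralisation step. Section 11.2 plans no adjustment for agent or time since dose.

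At stake is the one-month level in the recurrence regression. The percent change from baseline may be affected too: with no blood taken at Visit 1, Visit 2 may have to serve as the baseline. Enoxaparin and four oral agents are allowed (section 5.2), so any residual effect need not be the same in every patient. A sample drawn too early cannot be replaced at that time point.

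**Working it through.** No sample size, power or error rate in the plan depends on this point, so there is no stated figure to reproduce. The check compares the days that each timing statement allows.

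**Step 1. Visit 2 day relative to the stop of anticoagulation (stop = day 0).** For section 4.1 counted from the call, the day is 7 − c to 14 − c, where c is the number of days from call to stop. The plan does not state c, so the values below are assumptions.

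| Statement | Days allowed |
|---|---|
| Section 5.5 | 0 to +14 |
| Section 7 with section 5.2 | about 0 |
| Section 4.1, counted from the stop | +7 to +14 |
| Section 4.1, counted from the call, c = 3 | +4 to +11 |
| Section 4.1, counted from the call, c = 7 | 0 to +7 |
| Section 4.1, counted from the call, c = 14 | −7 to 0 |

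Of the two readings of section 4.1, only the count from the stop guarantees seven days. Sections 5.5 and 7 do not guarantee any gap.

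**Step 2. How long drug might remain.** The documents give no half-lives. For illustration only, assume first-order elimination with a half-life h of 6 to 18 hours. The fraction left after t hours is 0.5^(t/h).

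| Time since last dose | h = 6 | h = 18 |
|---|---|---|
| 12 h | 25% | 63% |
| 24 h | 6.25% | 39.7% |
| 48 h | 0.4% | 15.7% |
| 72 h | 0.02% | 6.25% |
| 168 h (7 days) | below 0.001% | 0.16% |

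On this assumption the problem is confined to roughly the first 2-3 days, and a seven-day gap removes it. These are fractions of drug remaining, not sizes of assay error.

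**Step 3. How many samples might be early.** Section 4.2 plans 36 patients at the Milwaukee site, the only one that draws blood. Assume visits spread evenly over 14 days.

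- Within 1 day: 1/14 = 7%, and 36 × 1/14 = 2.6.
- Within 2 days: 2/14 = 14%, and 36 × 2/14 = 5.1.
- Within 3 days: 3/14 = 21%, and 36 × 3/14 = 7.7.

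If section 4.1 is followed from the stop date, the number is about zero. If visits cluster at the point named in section 7, it is higher.

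**Step 4. The size of the analysis.** Section 10.4 cites recurrence of 14% and 20%. Applied to 36 patients, that gives 36 × 0.14 = 5.0 to 36 × 0.20 = 7.2 events. Fewer would be usable, because patients kept on treatment for a new thrombosis or an extension have no laboratory assessment (section 3.5). With so few events, a handful of distorted samples could matter. The same small number also means that the regression can only generate hypotheses.

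**The case against.** The best defence is section 4.1. Read together with section 5.5, its 1-2 weeks most naturally mean one to two weeks after stopping. It would then supply the lower limit and 5.5 the upper one. Section 7 is a payment list, and its one-month entry is a nominal label rather than a scheduling rule. Section 3.5 shows an intention to sample off drug. Medications are reviewed at each visit, so agent and stop date may already be captured; the appendix forms are not available to confirm this.

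Most of this stands, and it limits the point. It does not close the gap: section 5.5 is where the windows are set, it allows day 0, and section 4.1 does not say from when it counts.

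A reader might infer that all 36 Milwaukee samples are contaminated, or that the biomarker aim fails. The documents support neither. All 36 patients fall under the open window, but only draws soon after the last dose are at risk. Section 3.5 names no assay, agent or direction of effect, so a specific bias in thrombin generation or D-dimer cannot be asserted from the plan. Biomarker prediction is not among the clinical or secondary endpoints in sections 11.1.2 and 11.1.3. The biomarker feasibility endpoint, obtaining 80% of samples, is unaffected by residual drug.

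**Conclusion.** The point holds in a limited form. As written, section 5.5 permits the first research draw from day 0 to day 14 after stopping, and the one statement that might impose a gap is ambiguous. By the protocol's own reasoning, draws soon after the last dose could distort the one-month level, and also the percent change if Visit 2 is its baseline.

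The documents give neither the number of early draws nor the size of any shift. The figure of about 5 to 8 of 36 rests on evenly spread visits and on treating the first 2-3 days as the period at risk, which in turn rests on an assumed half-life of 6-18 hours. The analysis affected is exploratory and single-site. The post-thrombotic syndrome endpoint and the sample size are untouched. The change is still worth making, because it costs almost nothing and the samples cannot be retaken.

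**What to change.** - Reconcile sections 4.1, 5.5 and 7 into one Visit 2 window for the research draw, with the 1-2 weeks of section 4.1 counted explicitly from the last anticoagulant dose.
- Say in section 11.2 that the one-month level means this sample. With one month taken as 30 days, it falls on about days 37 to 44 after removal (30 + 7 to 30 + 14). State also which sample is the baseline for percent change.
- Record the agent and the date and time of the last dose, if the existing medication forms do not already do so.
- Flag samples drawn earlier than one week after the last dose and run the regression with and without them. Keep counting them toward the 80% collection target, so that the rule does not work against the feasibility endpoint.

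The cost is protocol wording, at most a small addition to one form, and slightly less flexible scheduling. No visit is added, and no change to treatment is implied.

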### 5.6 Blood measurements

Blood will be collected by venipuncture using a 20G needle or larger from patients at the BCW site at Visit 2, 3 and 4. A 21G needle may be used for collection of blood via venipuncture if blood cannot be obtained with a 20G needle or larger. The first 2 ml of blood will be discarded due to tissue factor activation with the venipuncture. Three BD Vacutainer citrated tubes (0.105M sodium citrate) with 4.5 ml blood will be collected. Thrombin generation, D-dimer, plasma total TFPI and TFPI $\alpha$ , and platelet TFPI $\alpha$ , will be assayed using platelet-poor plasma (PPP). Thrombin generation will also be assayed using platelet rich plasma (PRP). Laboratory procedures as noted in section 6.

